### 5.4 Handling of Dropouts, Missing Data, and Data Discrepancies

#### 5.4.1 Missing Tissue Eosinophil Count at Week 24

Eosinophil counts will be set to missing if they are collected after subjects have experienced ICE. Subject with missing Week 24 tissue eosinophil count for any reason will be imputed with the eosinophil count collected from the post-baseline unscheduled visit prior to missing. If no eosinophil count is collected post-baseline, the subject will be considered treatment failure for tissue eosinophil response.

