8.1 Prohibited Medications

Any biologics or medications that may interfere with the study, such as swallowed corticosteroids, systemic corticosteroids, and systemic immunosuppressive or immunomodulatory drugs (including azathioprine, JAK inhibitors, 6-mercaptopurine, methotrexate, cyclosporine, tacrolimus, anti-TNF, anti-IL-4 receptor (e.g., dupilumab), anti-IL-5 (e.g., mepolizumab), anti-IL-5 receptor (e.g., benralizumab), anti-IL-13 (e.g., lebrikizumab), anti-IgE (e.g., omalizumab), are prohibited for the duration of study participation.

The use of systemic or topical corticosteroids with a dose of >10 mg/day of prednisone or equivalent is prohibited unless it is due to unforeseen circumstances when it is deemed to be medically necessary to treat an unrelated medical condition or when given as a premedication prior to infusion or to treat an IRR that occurs during infusion. Any medications used for the treatment of IRR are not considered deviations from the protocol.

Subjects will be reminded to not take prohibited medications and to notify the site immediately if a prohibited medication is prescribed by another health care provider.

If medically necessary, rescue medications (systemic and/or swallowed topical corticosteroids) or emergency esophageal dilation may be used as rescue therapy. Any subject requiring rescue therapy must have an EGD (with biopsy collection and EREFS scoring) done prior to initiation

of rescue medications (or at the time of emergency esophageal dilation). The EGD performed due to initiation of rescue therapy will be used in place of the EGD scheduled for Day 169 (Week 24), and the subject will not have an EGD performed at the Day 169 (Week 24) visit. Subjects receiving rescue therapy should remain blinded, continue to receive study drug, and continue to comply with all study visits and assessments in accordance with the Schedule of Events (Table 1).

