15.7.1 Primary Efficacy Endpoint Analysis

The first co-primary endpoint is the proportion of subjects who achieve a peak esophageal intraepithelial count of ≤ 6 eosinophils/hpf at Week 24. The endpoint will be analyzed using Fisher's exact test comparing the AK002 group and placebo group for the proportion of treatment responders. Subjects who experience an ICE (e.g., exit the study prematurely or initiate prohibited/rescue medication or therapeutic EGD procedure) prior to the end of Week 24 will be treated as non-responders.

The second co-primary endpoint is the mean change in DSQ score from Baseline to Weeks 23-24. The DSQ score will be analyzed using ANCOVA with treatment as a factor, and Baseline DSQ and age strata (12-17, ≥ 18) as covariates. The Baseline DSQ will be calculated using the DSQ scoring algorithm for all daily DSQ assessments collected during the 2 weeks prior to the first infusion of study drug.

Data on subjects who experience an ICE (e.g., exit the study prematurely or initiate prohibited/rescue medication or therapeutic EGD procedure) prior to the end of Week 24 will be set to missing. Missing DSQ will be imputed using the Markov Chain Monte Carlo (MCMC) method.

Two sensitivity analyses will be conducted for the second co-primary endpoint. The first sensitivity analysis will be based on the placebo-based pattern-mixture model for the missing data imputation under the missing not at random (MNAR) assumption. In this model, subjects from the active treatment group after the ICE are assumed to behave like the subjects from the placebo group. Their missing data are imputed using the response profile from the placebo subjects who have similar baseline covariates and prior response trajectory. The second sensitivity analysis will utilize the tipping point method. In this method, the missing biweekly DSQ will be imputed with different adjustments for the active treatment subjects and placebo subjects under the MNAR assumption in search for a tipping point that reverses the study conclusion (i.e., p-value no longer < 0.05 for the treatment effect).

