- 14) An EGD with biopsy collection will be performed during screening and at Day 169 ( $\pm 3$  days). EGD biopsies will be collected, processed, and shipped in accordance with Protocol Appendix 9, the lab manual, and the histology manual. Day 169 biopsy results will be blinded. If ET occurs after Day 29 and before Day 169, an EGD with biopsy collection should be done 28 ( $\pm 3$ ) days after the last dose (as part of the ET visit, see Table Note 32). If rescue therapy is required, an EGD (biopsy and EREFS) must be done prior to initiation of rescue medication or at the time of emergency dilation (instead of at Day 169).
- 15) During the Screening EGD and Day 169 EGD, severity will be evaluated using the EoE Reference Score for Endoscopic Abnormalities per the study histology manual.
- 16) Please see the study central laboratory manual for collection, processing, and shipment instructions. If possible, samples should be shipped on the same day as collection.
- 17) Blood for serology (Hepatitis B surface antigen, Hepatitis C antibody, Hepatitis B core antibody, and HIV) will be obtained during screening.
- 18) For female subjects, blood will be obtained during screening to test for hCG (pregnancy) and FSH (post-menopausal status).
- 19) Blood for total serum IgE will be obtained on Days 1 (predose), 85 (predose), and 169 or ET, if subject early terminates before Day 169.
- 20) Blood for CBC with differential will be obtained at all study visits. On Days 1, 29, 57, 85, 113, and 141, blood will be drawn twice (predose and 1-hour postdose). For every CBC with differential blood collection except screening and Day 1 (predose), the blood count results will be blinded to the Sponsor and the site. The safety monitor may request an unscheduled CBC with differential. Blood counts from Day 197 will be used to determine if extended follow-up is needed.
- 21) Blood for chemistry will be obtained during screening, predose on dosing days (Days 1, 29, 57, 85, 113, 141), and on Days 169 and 197 (or ET).
- 22) Blood for PK will be obtained on Days 1, 8, 15, 29, 57, 85, 113, 141, 169, and 197 (or ET). Blood will be drawn predose on Days 1, 29, 57, 85, 113, and 141.

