#### **4.2.4 Intercurrent Events**

The events below are considered intercurrent events (ICE) confounding with the efficacy outcomes.

- Premature discontinuation from the study
- Use of prohibited/rescue medication
- Any therapeutic EGD (defined as dilatation or other intervention for a narrowing or stricture of the esophagus) at any point during the study through Week 24.

Further clarification and handling of ICE including prohibited/rescue medications is detailed in [Appendix 2](#).

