#### **4.2.5 Strategy for Handling Intercurrent Events**

Per the study protocol, if a prohibited medication is started during the course of the study, the subject will be withdrawn from study treatment and followed for the 12-week follow-up period. In addition, the follow-up EGD may not be performed. Thus, for analysis of the trial product estimand, tissue eosinophil values and DSQ scores will be counted as non-responders for binary variables and set to missing for continuous outcomes from the point when an ICE occurs. An appropriate method for handling missing data through statistical modeling (e.g., multiple imputation [MI]) will be used (Sections [5.4.1](#), [5.4.2](#), and [6.11](#)). The estimand will provide an answer to the question that is crucial to individual subjects:

“If I take this study drug as part of my treatment regimen, without adding any further medications or the use of therapeutic endoscopic interventions that may impact the underlying disease or exit the study prematurely, what improvements in histology and PRO symptoms might be anticipated after 24 weeks?”

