#### **6.11.1 Analysis of the First Co-Primary Endpoint**

The first co-primary endpoint will be analyzed using the imputed data set (Section 5.4.1). Fisher's exact test (primary analysis) will be conducted comparing AK002 with placebo for the proportion of tissue eosinophil responders. Proportion of responders and the associated 95% CI will be presented for each treatment group. The between group difference (pairwise comparison with placebo) and the associated 95% CI will also be computed and presented. A sample SAS code is as follows.

```

* COMPUTE 95% EXACT CONFIDENCE INTERVAL FOR %RESPONSE FOR INDIVIDUAL
TREATMENT ;
ods output BinomialCLs=CL ;
proc freq data=ADEF ;
    table RESP / out=CNTS bin(cl=midp) ;
    by TRTAN ;
run;

* COMPUTE 95% EXACT CONFIDENCE INTERVAL AND FISHERS EXACT P-VALUE FOR
BETWEEN TREATMENT DIFFERENCE ;
ods output FishersExact=PVAL(where=(name1='XP2_FISH'))
RiskDiffCol2=DIFF(where=(row='Difference')) ;
proc freq data=ADEF ;
    table TRTPN*RESP / riskdiff(cl=exact) exact ;
run ;

```

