## 9.2 Appendix 2: Intercurrent Events

- A. Use of any of the following prohibited medications during the course of the study as described:
- 1) Immunosuppressive or immunomodulatory drugs (e.g., IL-5 modulators, i.e., benralizumab, reslizumab, mepolizumab; IL-4 and IL-13 antagonists, i.e., dupilumab; calcineurin inhibitors, i.e., cyclosporin, tacrolimus; mTOR inhibitors, i.e., sirolimus, everolimus; anti-metabolites, i.e., azathioprine, methotrexate, 6-mercaptopurine, leflunomide, mycophenolate mofetil; alkylating agents, i.e., cyclophosphamide; TNF inhibitors, i.e., infliximab, adalimumab; anti-IgE antibodies, i.e., omalizumab; and eosinophil depleting drugs, i.e., pramipexole).
    - a) Use at any point during the study.
  - 2) Glucocorticoids
    - a) Initiation of any course of treatment or single use of systemic or swallowed corticosteroids at a dose of  $>10$  mg/day of prednisone or equivalent starting at Week 21 and through the end of Week 24. This does not include use of corticosteroids given as pre-infusion prophylaxis or treatment of IRR.
- B. Use of restricted medications outside the protocol-defined specifications
- 1) Glucocorticoids
    - a) Discontinuation of a previously stable dose of systemic or swallowed corticosteroids ( $\leq 10$  mg/day of prednisone or equivalent) after the screening period.
    - b) Initiation of systemic or swallowed corticosteroids ( $\leq 10$  mg/day of prednisone or equivalent) following the screening period and continuing to at least Study Week 21 (within 2 weeks of efficacy assessment at Weeks 23 and 24).
  - 2) Proton Pump Inhibitors
    - a) Discontinuation of a previously stable dose of an oral PPI after the screening period and before the end of Week 24.
    - b) Initiation or increase in the dose of an oral PPI following the screening period and continuing to at least Study Week 21 (within 2 weeks of efficacy assessment at Weeks 23 and 24).

- 3) Sodium cromolyn
  - a) Discontinuation of a previously stable dose of sodium cromolyn after the screening period and before the end of Week 24.
  - b) Initiation or increase in the dose of sodium cromolyn following the screening period and continuing to at least Study Week 22 (within 1 week of efficacy assessment at Weeks 23 and 24).

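### SAP 5.4.1 can score a rescued subject as a histologic responder from the biopsy taken just before rescue medication, where SAP 4.2.5 and Protocol 15.7.1 score a non-responder

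*SAP*

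**What the plan says.** **The imputation rule.** SAP 5.4.1 discards eosinophil counts obtained after an ICE. It then states: "Subject with missing Week 24 tissue eosinophil count for any reason will be imputed with the eosinophil count collected from the post-baseline unscheduled visit". The only route to failure is having no post-baseline count at all. SAP 6.11.1 makes this the primary analysis: "The first co-primary endpoint will be analyzed using the imputed data set (Section 5.4.1").

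**The estimand rule.** SAP 4.2.5 says that after an ICE, outcomes are "counted as non-responders for binary variables and set to missing for continuous outcomes from the point when an ICE occurs". SAP 4.2.4 lists rescue medication among the ICEs. Protocol 15.7.1 says that subjects who "initiate prohibited/rescue medication or therapeutic EGD procedure) prior to the end of Week 24 will be treated as non-responders".

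**The rescue biopsy.** Note 14 to SAP Table 1 requires that "an EGD (biopsy and EREFS) must be done prior to initiation of rescue medication or at the time of emergency dilation". Protocol 8.1 adds: "The EGD performed due to initiation of rescue therapy will be used in place of the EGD scheduled for Day 169 (Week 24"). A rescued subject has no separate Week 24 endoscopy.

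**Which rescue is an ICE.** SAP 4.2.4 passes the detail on: "Further clarification and handling of ICE including prohibited/rescue medications is detailed in" Appendix 2. That appendix counts systemic or swallowed corticosteroids above 10 "mg/day of prednisone or equivalent starting at Week 21 and through the end of Week 24". It also lists a course at or below 10 mg/day that begins after screening and runs to at least Week 21.

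**The concern.** Taken in order, these rules give opposite answers for one subject. The rescue biopsy comes before the drug, so it comes before the ICE and survives the deletion step. It then supplies the Week 24 count, and the failure route is never reached. A count of 6/hpf or lower makes the subject a responder under SAP 5.4.1 and 6.11.1, and a non-responder under SAP 4.2.5 and Protocol 15.7.1.

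The response rates, their difference and the confidence interval are the estimand's declared summary measures (SAP 4.2.6). Two programmers following different SAP sections would code this subject differently, and the independent reprogramming in SAP Section 7 cannot say which is right. No planned output would show the effect: the only sensitivity analysis for this endpoint is an optional stratified CMH test (SAP 6.11.2), which changes the test and not the ICE handling.

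The rule also reaches the ≤1/hpf and <15/hpf endpoints (SAP 6.12.2) and the histology half of the treatment-responder endpoint (SAP 6.12.3), because both sections refer back to 6.11.1.

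**Working it through.** **1. The plan's own figures.** SAP 3.6 gives 8 per group for 90% versus 10% response at 90% power, two-sided 0.05. Exact power of Fisher's test is 84.2% at 7 per group and 93.2% at 8, so 8 reproduces. The second co-primary endpoint sets the trial size: for a difference of 7.5 and an SD of 15, t-test power is 89.99% at 85 per group and 90.3% at 86. Then 86 / (1 − 0.14) = 100 per group.

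**2. One rescued subject with a pre-rescue count of 6/hpf or lower.**

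| Rule | Week 24 status |
|---|---|
| SAP 5.4.1 with 6.11.1 | Responder |
| Rescue EGD taken directly as the Week 24 value (Protocol 8.1) | Responder |
| SAP 4.2.5 | Non-responder |
| Protocol 15.7.1 | Non-responder |

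**3. Scope.** SAP Table 2 counts study weeks in sevens from Day 1. Week 21 starts on Day 20 × 7 + 1 = 141, and Week 24 ends on Day 24 × 7 = 168.

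- *Inside the SAP*, the conflict covers rescue that Appendix 2 counts as an ICE: above 10 mg/day started on Days 141–168, or a lower-dose course begun after screening and continuing to at least Week 21.
- *Between the documents*, rescue above 10 mg/day started before Week 21 is a separate difference. Protocol 15.7.1 calls it non-response; Appendix 2 does not list it as an ICE.
- Emergency dilation is left aside. Its biopsy is taken at the time of the event, so its order is not settled.

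**4. Size.** Let r be the share of an arm rescued with a pre-rescue biopsy, q the response rate in those biopsies, and p the response rate in everyone else. From SAP 3.6, pA = 0.90 and pP = 0.10. Neither r nor q is in the documents; both are assumed.

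- Current rule: p(1 − r) + rq in each arm.
- Non-responder rule: p(1 − r) in each arm.
- Change in the treatment difference: rA·qA − rP·qP.

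At 100 per arm, each rescued active subject with a count of 6/hpf or lower adds 1 point to that arm's rate.

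| rA / rP | qA / qP | Difference, current rule | Difference, non-responder rule | Change (points) |
|---|---|---|---|---|
| 1% / 1% | 90% / 10% | 80.0 | 79.2 | +0.8 |
| 2% / 2% | 90% / 10% | 80.0 | 78.4 | +1.6 |
| 5% / 5% | 90% / 10% | 80.0 | 76.0 | +4.0 |
| 1% / 1% | 45% / 10% | 79.55 | 79.20 | +0.35 |
| 2% / 2% | 45% / 10% | 79.10 | 78.40 | +0.70 |
| 5% / 5% | 45% / 10% | 77.75 | 76.00 | +1.75 |
| 1% / 1% | 0% / 10% | 79.10 | 79.20 | −0.1 |
| 2% / 2% | 0% / 10% | 78.20 | 78.40 | −0.2 |
| 5% / 5% | 0% / 10% | 75.50 | 76.00 | −0.5 |
| 2% / 5% | 90% / 10% | 80.0 | 78.7 | +1.3 |
| 2% / 5% | 20% / 10% | 78.6 | 78.7 | −0.1 |

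**5. Power.** Exact two-sided Fisher power at 100 per arm exceeds 99.9% at 90% versus 10%, 89.1% versus 9.9%, 88.2% versus 9.8%, 85.5% versus 9.5%, and 88.2% versus 9.5%.

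**The case against.** The strongest reply is that the sections are not of equal rank. SAP 6.11.1 names one data set, and 4.2.5 is estimand narrative that itself points to 5.4.1 for implementation. Its wording can be read as covering only values after the ICE, which is what 5.4.1 removes. That reading is possible, but Week 24 status lies after the ICE, and Protocol 15.7.1 classifies the subject rather than the value. No SAP text gives 5.4.1 priority.

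SAP 4.2.5 also rests on a premise that does not fit rescue here: withdrawal from treatment, a 12-week follow-up, and an endoscopy that may be skipped. Protocol 8.1 has the rescued subject continue study drug and undergo a mandatory EGD. This weakens 4.2.5 as authority, and it is a further reason to repair the text.

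The SAP supersedes the protocol's statistical methods (SAP Section 1, Protocol 15.1), so the protocol difference has a precedence rule. True, but that leaves the contradiction inside the SAP where it is.

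If the rescue EGD simply is the Week 24 value, the carry-forward is not the mechanism. The subject is still scored a responder, and limiting the carry-forward alone would not help. An explicit statement about ICEs is needed.

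The case is narrow, and this point stands. No routine biopsy falls between screening and Day 169, so for most other ICEs both rules end in failure. The window above 10 mg/day is 28 of 168 days. If rescue timing were uniform (an assumption), r = 5% in that window would imply 5% × 168/28 = 30% rescued overall, more than twice the planned 14% dropout; 1% and 2% would imply 6% and 12%. The 4.0-point figure is therefore hard to reach from that window alone. Appendix 2's commentary also calls the lower-dose route only a potential ICE.

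**Conclusion.** The concern holds. As written, the SAP gives two incompatible classifications for a subject whose tissue count is at or below the threshold just before rescue medication, and the primary analysis follows the one that disagrees with the stated estimand.

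The effect is on estimation. Under equal rescue and the planning response rates, the treatment difference is overstated by 0.80 × r. The direction is not certain: the change shrinks or reverses if rescued active subjects respond poorly or if rescue is more common on placebo. All sizes rest on assumed r and q, and the smaller values of r are the more plausible for the conflict inside the SAP. Significance and power for this endpoint are not at risk. The matter should be fixed before unblinding, because choosing the rule afterwards would look driven by the result.

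**What to change.** Add one sentence to SAP 5.4.1: *A subject with an ICE before the end of Week 24 is a non-responder for all binary histology endpoints and for the treatment-responder endpoint, whatever earlier biopsy exists.* Limit the carry-forward to Week 24 counts that are missing without an ICE. Report the current 5.4.1 rule as a labelled sensitivity analysis.

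Separately, reconcile the corticosteroid window in Appendix 2 with Protocol 15.7.1 for analysis purposes. Until that is done, rescue above 10 mg/day before Week 21 is still scored from the pre-rescue biopsy even with the new sentence. Nothing here takes a position on the clinical rescue rule.

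The cost is SAP wording and slightly lower reported rates. They fall by rA·qA in an active arm and rP·qP on placebo: at the planning rates, 1.8 and 0.2 points if r is 2%, and 4.5 and 0.5 points if r is 5%. A rescued subject whose tissue had cleared counts as a failure in the primary analysis, and the sensitivity analysis shows the alternative. No new data are needed, and Fisher power stays above 99.9%.

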#### 5.4.2 Missing Daily PRO Scores at Weeks 23–24

The PRO daily scores will be set to missing if they are collected after subjects have experienced an ICE. For the endpoint of change in the biweekly DSQ score, the biweekly average score will be calculated using the available daily scores. The validated DSQ calculation normalizes the missing daily scores within the 14-day, biweekly interval.

Missing DSQ scores during Weeks 23–24 will be imputed using the MCMC method. Baseline tissue eosinophil count and baseline DSQ and age strata will be included along with the average biweekly DSQ (W01\_02, W03\_04, W05\_06, ..., W21\_22, W23\_24) in the multivariate distribution construction. The imputation will be carried out for each treatment group separately and will be executed multiple (50) times (MI). The purpose of MI is to account for the imputation variability in the parameter estimates. Missing data imputation (PROC MI) will be conducted separately for active AK002 treatment groups. An example of the SAS code for this imputation follows.

```
proc mi data=DSQ seed=1357986420 nimpute=50
  out=DSQ_IMPUTED ;
  by TRTMT ;
  class AGE_STRATA;
  mcmc chain=multiple impute=full initial=em nbiter=200 niter=100 ;
var B_EOS B_DSQ DSQ_W01_02 DSQ_W03_04
... DSQ_W21_22 DSQ_W23_24 ;
run ;
```

After imputation, the LSM and SE are derived from the conventional ANCOVA from each imputed data set. These LSM and SE are synthesized to derive the imputation variability-adjusted LSM and SE for each treatment group and for the between treatment difference.

These synthesized LSM and SE are then used in the hypothesis test for the between treatment difference. An example of the SAS code for the synthesized LSM comparisons between treatment is as follows.

```
ods output ParameterEstimates=LSMDIF ;
proc mianalyze data=LSMDIFF alpha=0.05 ;
  by trtmt;
  modeleffects LSM ;
  stderr SE ;
run ;
```

### 5.4.3 Missing or Partial Dates of Adverse Events or Concomitant Medications

Adverse events with incomplete start or stop dates (i.e., either day or month is missing) will be considered treatment-emergent adverse events (TEAE) unless the partial start date or the stop date confirms the AE started or ended prior to Study Day 1 (e.g., the day of the AE start date is unknown but the month and year indicate that the AE starts prior to Study Day 1). Adverse events with missing relationship to study drug will be included in the “Related” category for the summary tables and footnoted. Adverse events with missing severity will not be included in the by-severity summary table but will be footnoted in the table.

When there is incomplete information regarding dosing dates for prior and concomitant medication, the medication will be considered as a concomitant medication unless it contradicts with the stop date. For example, a medication will be considered a prior medication if the month and year of the end date indicates a date before Study Day 1 even though the start date could be missing.

